GCP	Good Clinical Practice	10.3.1
GET Living	Graded in-vivo Exposure Treatment	1.1, 2.1, 2.2, 3, 4.3, 5.1, 5.2, 5.4, 6.2.1, 6.2.2, 6.2.5, 9.1, 9.2, 9.6, 10.3.1
HBE	Home-Based Exposure	5.1
IFAM	Interpersonal Fear Avoidance Model	2.1, 5.1
ICH	International Conference on Harmonisation	10.3.1
IRB	Institutional Review Board	7.4, 7.5, 7.6, 10.3.4, 11.1, 11.3, 11.4
JFM	Juvenile Fibromyalgia	2.1
MSPL	Motion and Sports Performance Laboratory	10.2
NIAMS	National Institute of Arthritis and Musculoskeletal and Skin Diseases	7.4, 10.3.4, 11.3, 11.4
NIH	National Institutes of Health	10.3.1, 13
OHRP	Office for Human Research Protections	11.3, 11.4
PA	Physical Activity	2.1
PD	Protocol Deviation	10.3.4
PHODA-YE	Photographs of Daily Activities – Youth English	2.2, 5.1, 9.5.1, 9.5.5
PI	Principal Investigator	7.4, 8, 10.3.2, 10.3.4, 12
PID	Participant Identification Number	11.3
PPMC	Pediatric Pain Management Clinic	3, 5.1, 6.2.1
PROMIS	Patient-Reported Outcomes Measurement Information System	4.1
PSY	Psychology/Psychologist	5.1, 10.3.1
PT	Physical Therapy/Therapist	3, 5.1
RC	Research Coordinator	6.2.1, 6.2.2
REDCap	Research Electronic Data Capture	6.2.2, 7.4, 10.1, 10.2
SAE	Serious Adverse Event	7.3, 7.4
SCH	Stanford Children's Health	3, 5.1, 6.2.1, 10.2
S.M.A.R.T.	Specific, Measurable, Achievable, Relevant, Time-Bound	5.1
SMC	Safety Monitoring Committee	7.4, 7.6, 10.3.4
TPM	Typical Pain Management	1.1, 2.1, 3, 4.3, 5.1, 6.2.2, 6.2.5, 9.1, 9.2, 9.6
SR	Self-Report	3
UP	Unanticipated Problem	7.3, 7.4
WILD	Willingness, Importance, Likelihood of Success, Degree of Difficulty	2.2, 5.1

PARTICIPATING STUDY SITES

The study will be conducted at Stanford Children's Health Facilities.

PRÉCIS

Study Title

GET Living: Graded Exposure Treatment for Adolescents with Chronic Musculoskeletal Pain

Objectives

Reducing elevated pain-related fear promotes participation in daily activities¹⁻⁴. When patients experience how disengagement from safety behaviors does not lead to catastrophic consequences, their misinterpretations are challenged and disconfirmed, enabling them to correct their fear expectancies⁵⁻⁷. **GET Living** is the first program to explicitly targeted pain-related fear and associated disability in adolescents. Currently, most rehabilitative treatments for adolescents with chronic pain involve promoting pain coping strategies via psychology with separate physical therapy prescribed. Unfortunately, the debilitating influence of pain-related fear can stymy progress in both domains resulting in continued high healthcare utilization without symptomatic improvement.

Design and Outcomes

This study will be a randomized control trial (RCT) including approximately 74 children, ages 8-18, with musculoskeletal pain who present for treatment at Stanford Children's Health (SCH).

A “**participant**” in this study is defined as a child and at least one parent. The term “*patient*” is used to describe the child participant only. Participants will attend an initial baseline assessment (BAS) to perform consent/asset, undergo a biomechanical assessment by the Motion and Sports Performance Laboratory of SCH, and complete self-report questionnaires. Child participants will also be given an Actigraph and will be introduced to the daily diaries. Following BAS, participants will undergo a pre-treatment baseline period where daily diaries will be collected and Actigraphy monitoring will occur. After the baseline period, participants will be randomly assigned to a treatment group, Graded Exposure Therapy (GET Living) or Typical Pain Management (TPM) stratified on their fear and disability scores. Participants in the GET Living intervention group (n=37) will engage in 1-hour sessions of GET Living for 12 sessions jointly facilitated by a pain psychology therapist and physical therapist. Participants randomized into the TPM treatment group (n = 37) will engage in 6 sessions of cognitive behavioral therapy and 6 sessions of physical therapy following BAS. Parents enrolled into the TPM arm will engage in 3 parent-only sessions with the child’s cognitive-behavioral therapist. All participants complete a Daily Diary during treatment.

At treatment discharge for the GET Living intervention group and TPM treatment, participants will undergo a second biomechanical assessment and complete self-report questionnaires. After completion of the second assessment evaluation, participants are contacted for follow-up evaluation, which includes completion of the Daily Diary for a 7-day window and self-report questionnaires at each follow-up time point (3 and 6 months post-second assessment).

Interventions and Duration

The GET Living intervention will be compared to Typical Pain Management (TPM) provided at Stanford Children's Health. Each participant will be enrolled in the study for up to 40 weeks – Starting with the BAS visit, 2 weeks (on average) of a pre-treatment baseline period, approximately 6 weeks of active treatment, Discharge Assessment, and 3 and 6-month post-discharge follow-up. (See Figure 3 for a break-down of the study milestones and expected timeline.)

Sample Size and Population

An ideal recruitment site, Stanford houses a tertiary care pediatric pain management treating approximately 300 unique patients in the clinic each year. Patients who meet eligibility criteria will be informed of the study by their pain clinicians at clinic appointments and provided a study brochure. We aim to recruit a total of 74 participants into the study.

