
biostatistician will also create a randomization scheme to determine the number of days for the pre-treatment baseline period for each individual participant (2 weeks on average).

Study Procedures. At the BAS visit participants will complete informed assent/consent, complete baseline questionnaires, begin daily diaries, and begin wearing an Actigraph. Child participants will undergo biomechanical assessment (**[name]**, Director of the Motion and Sports Performance Laboratory at SCH) during this visit. Notification of treatment arm allocation will occur at the end of the pre-treatment baseline period, and treatment will begin according to randomized group allocation: GET Living or TPM. Discharge testing occurs at the end of GET Living or TPM and includes participant questionnaires, child biomechanical assessment, and an exit interview. Daily diary and actigraphy ends at discharge. At 3 and 6 months follow-up, participants complete daily diaries for 7-days and self-report questionnaires.

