6.2.6 Follow-Up Assessments

A set of self-report measures will be completed by **all participants** (child & parent) after 3 and 6-months post-discharge.

See Supplemental Materials III for follow-up assessment measures

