8. INTERVENTION DISCONTINUATION

Patients and their parents have the right to withdraw consent/assent or discontinue participation at any time without penalty or any impact on the child's care. Because this is an exploratory clinical trial, we will not discontinue participation based on missed attendance to treatment sessions. There will be no temporary discontinuations from treatment or study participation. The PI may withdraw a patient/parent dyad from the study for one or more of the following reasons:

- Failure to follow instructions of the PI or study staff.
- The PI decides that continued participation would be harmful (e.g., patient reports increased emotional or physical distress from exposure therapy)

Patients and parents will be asked permission to use data collected from the study if they are asked to discontinue or decide to withdraw from the study.

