9.2 Sample Size and Randomization

We chose the largest feasible study size to obtain as precise estimates as possible of improvement in adolescent disability while ensuring adequate power for the treatment difference in the improvement in adolescent pain-related fear. This gave us a starting total sample size of 74 (37 in each arm). Based on pilot data, we expect roughly 19% attrition during treatment to a total of 60 and further attrition to 58 at end of follow-up.

Power calculations were first performed using the simplified approach of paired t-tests for the change from baseline to 3 and 6-months on those with 3 and 6-months data. For this approach, we used means and standard deviations of observed changes in pilot data. We then simulated data from our analytic model using the standard deviations at each time point and standard deviations of change to calculate correlation and hence the random effect and error variances. The mixed models simulation allowed us to use more data and yielded slightly higher power estimates.

Primary Outcome: In our primary power calculation, we assumed that the improvement in adolescent pain-related fear at 3 and 6-months would be 22.4 in GET Living and 5 in TPM, a difference of 17.4, with a standard deviation for change of 21. Under this scenario we will have power of 87% with 58 (29 in each arm) at end of study. Under more conservative assumptions, we still have power of 80% with only 52 at the end of study and a treatment difference of 16.6. With a smaller standard deviation of 18.9, we will have power of 80% with 50 at end of study and a treatment difference of 15.4.

Other Outcomes: For parent pain-related fear, our estimated treatment difference at 3 and 6-months is 13 with an estimated standard deviation for change of 8.5. This would give us power close to 100% for 58 at end of study and we would still have 90% power with a treatment difference of only 8 and only 50 left at end of study.

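### No assessment time is set for families who stop treatment early, so the pain-related fear comparison would in practice rest largely on completers

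*Combined protocol and SAP*

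**What the plan says.** Every full questionnaire after baseline is tied to discharge. Section 3 (Study Procedures) states "Discharge testing occurs at the end of GET Living or TPM". In the Précis (Design and Outcomes), follow-up contact comes next in the sequence: "After completion of the second assessment evaluation, participants are contacted for follow-up evaluation", with the visits timed "3 and 6 months post-second assessment". Section 5.1 repeats the discharge anchor for both arms, and section 6.2.6 has the follow-up measures completed "after 3 and 6-months post-discharge". Table 4 in section 6.1 has no early-termination visit.

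Two statements point towards keeping families in the study. Section 6.2.6 addresses the follow-up questionnaires to every participant, child and parent. Section 8 says "Because this is an exploratory clinical trial, we will not discontinue participation based on missed attendance to treatment sessions". On withdrawal, section 8 says only "Patients and parents will be asked permission to use data collected from the study if they are asked to discontinue or decide to withdraw"; it describes no further assessment.

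On numbers, section 9.2 says "we expect roughly 19% attrition during treatment to a total of 60 and further attrition to 58 at end of follow-up", starting from 74. Section 9.6 gives 18% by discharge and then 5%. Section 9.3 does not distinguish an intention-to-treat from a per-protocol set. Section 9.1 names a linear mixed effects model for the fear scores. No missing-data assumption is stated.

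**The concern.** A coordinator following this text has no date on which to send the fear questionnaires to a family that stops, say, at session 4. The discharge visit marks the end of a treatment the family did not finish, and the two later visits are counted from that visit. The likely result is that such a family contributes a baseline and nothing more to the primary comparison.

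That matters because leaving is unlikely to be unrelated to outcome. Section 8 itself gives increased distress from exposure therapy as an example of a reason for withdrawal, and that reason applies to one arm only. If those who leave GET Living gain less than those who stay, a comparison built on the stayers overstates the effect in everyone randomised. Section 2.1 says the trial is meant to support or refute a large multi-site trial, so the effect size will be carried forward. Outcomes that were never collected cannot be recovered at the analysis.

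**Working it through.** **Inputs.** Section 9.2: 74 randomised (37 per arm); 60 left after treatment and 58 at the end; improvement of 22.4 in GET Living and 5 in TPM; SD of change 21; stated power 87% with 29 per arm. Section 9.6: further loss of 5% after discharge. Significance level 0.05, taken as two-sided (the documents do not say).

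**Attrition.** 74 × 0.81 = 59.9, so 60. By section 9.6, 74 × 0.82 × 0.95 = 57.6, so 58. Thus 74 − 60 = 14 (18.9%) are lost during treatment and 74 − 58 = 16 (21.6%) by the end. The two sections agree in treating treatment drop-out as loss of outcome data.

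**The plan's own power.** Two-sample t-test on change scores, noncentrality d / (s√(2/n)), 2n − 2 degrees of freedom. With d = 17.4, s = 21, n = 29: 17.4 / (21 × 0.2626) = 3.16, power 87.3%. The stated 87% reproduces. At the final level of 0.0492 in section 9.4 it is 87.2%.

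**What the mixed model does with leavers.** Suppose leavers give only a baseline and leaving is unrelated to baseline fear. Then a group-by-time model has the completers' difference, here 17.4, as its expected value. That equals the all-randomised difference only if leavers would have changed like those who stayed in the same arm, which is what missing-at-random implies here.

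**What the all-randomised difference could be.** Assume the same fraction f = 14/74 = 0.189 leaves each arm, with SD 21 among both leavers and stayers. For GET Living leavers improving by g, the arm mean is 0.811 × 22.4 + 0.189 × g:
- g = 5: 18.16 + 0.95 = 19.1
- g = 0: 18.16 + 0 = 18.2 (rounded)

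Mixing leavers and stayers widens the arm's variance to 21² + f(1 − f)(22.4 − g)². For g = 5 this is 441 + 0.153 × 302.8 = 487.4. Averaged with 441 in TPM it gives a pooled SD of 21.55. For g = 0 the pooled SD is 21.90.

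For the number with data, assume leavers are followed with the same 5% loss as everyone else: 74 × 0.95 = 70.3, or 35 per arm.

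| Leavers' improvement (GET Living / TPM) | Difference, all randomised | Pooled SD | Power, 35 per arm |
|---|---|---|---|
| 22.4 / 5 (same as completers) | 17.4 | 21.0 | 92.7% |
| 5 / 5 | 14.1 | 21.55 | 77.0% |
| 0 / 0 | 14.1 | 21.94 | 75.5% |
| 0 / 5 | 13.2 | 21.90 | 69.8% |

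Against 17.4, the rows with TPM leavers at 5 fall short by 3.3 points (19%) and 4.2 points (24%).

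**The case against.** The strongest reply is that the plan leaves a gap and sets no rule against following leavers. The Précis sentence gives the usual order of events and does not say that only families with a completed discharge visit are contacted. Sections 6.2.6 and 8 point the other way, and section 9.3 defines no completer set. All of this stands. A reader might infer that the protocol bars leavers from follow-up, or prescribes a completer analysis; the documents support neither reading.

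A reader might also take section 9.2 as proof that leavers will not be assessed. It is a planning assumption drawn from pilot attrition. It shows how the sample size was reasoned, not whom staff will contact.

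The timing evidence has limits too. Figure 3 is not visible in the text reviewed and may show week-based timing. Section 9.2 also puts the end of the study assessments at 6.5 months after baseline, which is a baseline anchor. That anchor does not settle the matter: 6.5 months is about 28 weeks, whereas 2 weeks of baseline, 6 of treatment and 26 of follow-up make 34.

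It is also tempting to say that all questionnaires are already online. Table 4 labels only the 3- and 6-month visits so. The discharge visit includes laboratory motion analysis, and remote discharge questionnaires would be an addition.

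Finally, following leavers cannot be credited with both removing bias and raising power to 93%. The 93% applies only if leavers benefit fully, and in that case there was no bias to remove. The 5% loss among leavers is also optimistic. If half of the 14 were retained to discharge, about (60 + 7) × 0.95 = 64 would have data.

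What survives is that neither the statements of intent nor the mixed model gives an early stopper an assessment date, and the planning figures count those families as missing.

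**Conclusion.** The point holds as a gap with a foreseeable consequence. The plan dates all post-baseline questionnaires from the end of treatment, sets no time for families who stop early, and plans the sample size as if they yield no outcome data. Followed as written, the fear result would rest largely on completers and would describe everyone randomised only under an unstated missing-at-random assumption.

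The size is conditional. With 19% leaving each arm, the all-randomised difference is about 13.2 to 14.1 if GET Living leavers gain 0 to 5 points and TPM leavers gain 5, with power of about 70% to 77%. It is 17.4, with no bias, if leavers do as well as completers. These are illustrations and not bounds: leavers could worsen, and the leaving rate could differ by arm. The documents give no outcome data on leavers.

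**What to change.** In sections 6 and 8, state that stopping treatment is not leaving the study. Unless consent is withdrawn, collect the FOPQ-C, the parent fear measure and the FDI remotely from every randomised dyad, whether or not the discharge visit took place. Use a fixed end-of-treatment window counted from randomisation, and then 3 and 6 months after it. That window can be set only once sections 3 and 5.1 are reconciled: for GET Living, one allows up to 12 weeks of treatment and the other up to 6.

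In section 9.3, say that all randomised families are analysed in their assigned arm. In sections 9.2 and 9.6, give treatment drop-out and missing outcome data as two separate figures.

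The cost is protocol wording, a scheduling rule, remote delivery of the discharge questionnaires and extra reminders. The downside is that the effect and power quoted for all randomised families may be somewhat lower than those now stated.

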1.1 Primary Objective

1a. To evaluate pain-related fear outcomes between GET Living and TPM. Hypotheses: Compared to TPM, the GET Living group will (1) have significantly less pain-related fear avoidance (adolescent, parent) at discharge, with continued gains at 3 and 6-month follow-up; Exploratory: (2) have fewer number of days to pain-related fear avoidance improvement via daily diaries.

1b. To evaluate disability and parent responses to pain outcomes between GET Living and TPM. Hypotheses: Compared to TPM, adolescents receiving GET Living will have (1) significantly less functional disability and protective parent responses at discharge, with continued gains at 3 and 6-month follow-up; Exploratory: (2) fewer number of days to achieve decreased functional disability and protective parent responses, assessed via daily diaries; (3) significantly better adolescent joint kinetics at discharge, assessed via motion analysis; and (4) demonstrate significantly greater increases in daily physical activity levels at discharge via Actigraphy. We will also examine treatment response correlates: age, pain, gender, diagnosis, and readiness to change.

2. To characterize feasibility and acceptability of GET Living compared to TPM to inform implementation of a large multi-site RCT. Hypotheses: GET Living participants will have (1) high treatment satisfaction ratings (mean score \geq 40 of 60; reflective of satisfied or very satisfied); Secondary: (2) \geq 80% sessions completed on-schedule, \leq 20% attrition rate, \geq 80% adolescent and parent daily diary adherence; Exploratory: (3) fewer health care costs at 3 and 6-month follow-up compared to TPM.

2. BACKGROUND AND RATIONALE

2.1 Background and Significance

[figure not shown]
Overall Scientific Premise. Chronic musculoskeletal pain in adolescence is a significant public health concern with median prevalence rates of 11 to 38%^{8,9}, with 3 to 5% of adolescents suffering from significant pain-related disability^{10,11}, costing society \$19.5 billion annually in the US alone¹². Notwithstanding the personal suffering and persistent physical and economic consequences for families, chronic pain in adolescence can predispose the development of adult chronic pain¹³. Fear avoidance is a particularly salient influence on pain outcomes¹⁴⁻¹⁷ and is a risk factor for less treatment responsiveness¹⁸. Typical Pain Management (TPM) yields only modest improvements in functional disability and no change in pain-related fear avoidance¹⁹. These findings underscore the need to specifically target pain-related fear avoidance in adolescents to potentially avert sustained pain-related disability. *Thus, the current exploratory randomized controlled trial (RCT) tests graded in-vivo exposure treatment (GET) for adolescents with chronic musculoskeletal pain (GET Living).* While TPM focuses on pain control via pain management psychology and impairment-based physical therapy, GET Living is jointly delivered by a pain psychologist and physical therapist targeting functional improvement through exposing participants to activities previously avoided due to fear avoidance of pain or re-injury. Implementing GET Living will represent a significant treatment paradigm shift by focusing on a key mechanism (pain-related fear avoidance) rather than on pain itself. Knowing that RCTs of GET are successful in adults with chronic musculoskeletal pain^{2,3,20-24} and with compelling preliminary results from our pilot work of GET Living, *this exploratory RCT will provide the necessary findings to support or refute a large multi-site RCT serving as the basis for potential large-scale implementation of GET Living nationwide and ultimately expand effective, tailored treatment options for adolescents struggling with persistent musculoskeletal pain, fear, and disability.*

Scientific premise for GET Living. Reducing elevated pain-related fear promotes participation in daily activities¹⁻⁴. When patients experience how disengagement from safety behaviors does not lead to catastrophic consequences, their misinterpretations are challenged and disconfirmed, enabling them to correct their fear expectancies⁵⁻⁷. GET Living is the first program in the United States to explicitly targeted pain-related fear and associated disability in adolescents. Currently, most rehabilitative treatments for adolescents with chronic pain involve promoting pain coping strategies via psychology with separate physical

therapy prescribed. Unfortunately, the debilitating influence of pain-related fear can stymy progress in both domains resulting in continued high healthcare utilization without symptomatic improvement.

Scientific premise for addressing pain-related fear in adolescents and parents. Adolescent pain-related fear is associated with disability, depressive symptoms, and school impairment^{24,25}. Recent work has identified that it is equally important to assess and address parental fears. Parent emotional responses serve as key guides to a child's learning of safety and danger, in turn influencing subsequent behavior^{26,27}. Growing evidence supports parent pain catastrophizing and protective behavior in prioritizing pain control²⁸, higher functional disability^{29,30} and school dysfunction³¹ in youth with pain. Building from the Fear Avoidance Model of Pain³²⁻³⁴, we developed and validated the Interpersonal Fear Avoidance Model of Pain (IFAM) (Figure 1)³⁵. Within the IFAM, parents interpret an adolescent's pain expression through the lens of their own catastrophic appraisals and pain-related fears, and are more likely to engage in maladaptive parenting behaviors (i.e., protective responses), in turn negatively influencing adolescent pain-related function.

Figure 1. IFAM

Scientific premise for biomechanical assessment and physical activity monitoring. A cycle of fear of movement, activity avoidance, and abnormal movement patterns (kinesics) in adolescents with chronic pain can lead to decreased tolerance to physical activity that persists into adulthood³⁷. Abnormal kinesics, such as asymmetry in range of motion, or timing of muscle activation or joint motions, commonly exist as a compensatory mechanism in (adult) chronic pain^{38,39} and potentially amplified by pain-related fear⁴⁰. Adolescents with juvenile fibromyalgia (JFM) have higher fear of movement and greater variability in lower extremity mechanics during gait assessment and drop landing compared to healthy controls³⁷. Moreover, in a small pilot trial (n=11) of CBT and neuromuscular training in JFM, improvements were observed in walking gait (stride length) and functional performance (drop vertical jump)⁴¹. Building from work in JFM, examining biomechanics of gait and functional movements among a diverse group of chronic pain patients in this RCT allows us to precisely define the joint motions and forces that are altered by chronic pain, and the changes that occur with TPM compared to GET Living.

In order to understand the impact of altered biomechanics observed in the laboratory, this trial includes real world objective physical activity (PA) monitoring via a wrist-worn actigraph. Actigraphy is particularly useful as self-report measures can be prone to response shift and reporter bias^{42,43}. Unlike laboratory-based objective measures of physical activity, such as timed walks and peak oxygen consumption during exercise, actigraphy provides high ecological validity with unobtrusive measurement of activity levels during daily life⁴⁴. Adolescents with chronic pain have lower mean and peak activity levels compared to healthy peers⁴³. Although changes in physical activity via actigraphy have not been demonstrated for adolescent fibromyalgia patients using cognitive-behavioral therapy alone⁴⁵, it is hypothesized that the integrated GET Living approach will increase mean and peak physical activity levels.

Significance of the expected research contribution: (1) targeting pain-related fear, a key mechanism associated with pain-related dysfunction, (2) addressing parent distress and behavior to enhance adolescent

fear eradication, and (3) providing proof-of-principle of innovative daily tracking and biomechanical measures to define clinical endpoints and assess treatment progress within this clinical trial.

